trials. Once these metrics are computed per person, investigators will compute mean accuracy and reaction time for each stimulation condition, which will be the outcome metrics. Faster reaction times and higher accuracy reflect more favorable outcomes following the particular type of stimulation relative to sham and can be assessed using an ANOVA per measure with follow-up post-hoc testing to identify the specific direction of any significant effects. As per the MEG, the raw data will be transformed into the time-frequency domain and imaged, per participant, frequency band (alpha, gamma), and condition, using an advanced beamforming approach. The resulting images are comprised of neural response amplitude values in each of thousands of voxels (i.e., cubes of tissue). Investigators will then compare the amplitude of each voxel for stimulation effects using a whole-brain mass univariate approach in the Statistical Parametric Mapping (SPM12) software. The resulting statistical F-maps of neural oscillatory activity will reveal brain areas with significant differences by stimulation condition, and then use post-hoc testing will be used to derive the direction of the effect. In addition, investigators will extract the time series from these significant clusters by computing a virtual sensor at the peak voxel. These time series will enable us to compute the spontaneous activity level during the baseline period and this will be used to determine whether there are differences in spontaneous neural activity by stimulation condition. For these analyses, separate ANOVAs will be computed for each cluster. Note that all statistical analyses will be done separately for the alpha and gamma maps and multiple comparisons correction will use the Bonferroni method.

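### The spontaneous-activity ANOVA is run at a voxel picked by the same condition contrast, so it can exceed its nominal error rate unless baseline and response errors are uncorrelated

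*Combined protocol and SAP*

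**What the plan says.** All of this is in the combined protocol and SAP, under Primary Statistical Analyses. The beamformer images hold "neural response amplitude values in each of thousands of voxels". A whole-brain comparison by condition follows: "The resulting statistical F-maps of neural oscillatory activity will reveal brain areas with significant differences by stimulation condition", and "post-hoc testing will be used to derive the direction of the effect". Next, "investigators will extract the time series from these significant clusters by computing a virtual sensor at the peak voxel". The purpose is then given: "These time series will enable us to compute the spontaneous activity level during the baseline period". The level so obtained serves the comparison of interest, since "this will be used to determine whether there are differences in spontaneous neural activity by stimulation condition". The test is that "separate ANOVAs will be computed for each cluster". Alpha and gamma are analysed separately, with Bonferroni correction.

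The visit description in the Study Protocol section names spontaneous alpha and gamma activity among the outcome measures. The virtual-sensor ANOVA is the only test of spontaneous activity that the plan describes.

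**The concern.** The sensor goes where the anode/cathode/sham difference in response amplitude is largest. Part of that peak is chance: among many candidate voxels, the one with the most favourable error tends to win. Baseline activity at the same voxel, from the same sessions and in the same band, is then tested for the same factor. If its condition-contrast errors are correlated with those of the response, some of the selected chance difference passes into the baseline test. That test then starts from a difference that is not zero on average, although stimulation has no effect on spontaneous activity.

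Modulation of spontaneous activity is the question in the study title, so a miscalibrated test here bears on a central result. Bonferroni over clusters corrects for how many tests are run. It does not correct for how the voxel was chosen.

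**Working it through.** **The plan's own figure.** The plan states no error rate for this test. Its only recomputable design figure is 34 per group for d = 0.96, alpha 0.01 and power 0.90, under Sample Size Considerations. A two-sided two-sample t-test with 34 per group has power 0.9001, so the figure is reproduced. It matters here only as an indication of the effect size expected.

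**Inputs.** From the documents: 124 complete data sets, three conditions within participant, thousands of voxels, and a Bonferroni correction. The ANOVA F has 2 and 2 x 123 = 246 degrees of freedom. Assumed, because the documents do not say: map and ANOVA each at 0.05; 1,000 to 10,000 voxels; image smoothness; and rho, the correlation between the condition-contrast errors of response and baseline.

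**Plausible values of rho.** Suppose amplitude is the task-period value minus baseline, with equal variances and a task-baseline error correlation c. Then rho = (c - 1)/sqrt(2 - 2c).
- c = 0: rho = -1/sqrt(2) = -0.71.
- c = 0.71: rho = -0.29/sqrt(0.58) = -0.38.

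If amplitude is absolute, rho = c. The sign does not affect the ANOVA rejection rate.

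**Mechanism, for a cluster that is itself a false positive.** With 2 and 246 df, P(F > f) = (1 + f/123)^(-123). The critical F is 3.03 at 0.05 and 10.31 at 0.05/1,000. Given that the threshold is passed, the summed squared standardised contrasts are about 2 x (10.31 + 1) = 22.6. Baseline inherits rho² of this. For rho = 0.3 that is 0.09 x 22.6 = 2.04, so the numerator of the baseline F averages (2.04 + 2 x 0.91)/2 = 1.93 instead of 1. Simulated rejection at nominal 0.05, over 1,000 to 10,000 voxels:

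| rho | rejection |
|---|---|
| 0 | 0.05 |
| 0.1 | 0.065-0.070 |
| 0.2 | 0.12-0.13 |
| 0.3 | 0.21-0.25 |
| 0.5 | 0.53-0.64 |

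**Real oscillatory effect, independent voxels (1,000).** With an effect of 0.3 to 0.8 standardised units spread over 10 to 50 voxels, rejection is about 0.05 at rho 0, 0.06-0.09 at rho 0.3 and 0.08-0.14 at rho 0.5. With one true voxel and an effect of 0.5 or more, it is 0.05-0.06 even at rho 0.5.

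**Real oscillatory effect, smooth images.** These runs use 14³ = 2,744 voxels, a Bonferroni F-map and no true baseline effect, and count only trials with a cluster. Effects are in SD of the paired difference; FWHM is in voxels.

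| Setting | F-map peak | Averaged-map peak |
|---|---|---|
| Four settings: rho -0.71, FWHM 3 and 5, effect 0.28-0.35 | 0.219, 0.190, 0.099, 0.121 | 0.038, 0.045, 0.057, 0.058 |
| rho -0.71, FWHM 3, effect 0.3 | 48/189 (25%) | 18/189 (10%) |
| rho -0.71, FWHM 5, effect 0.35 | 18/198 (9%) | 11/198 (6%) |
| rho -0.71, FWHM 3, effect 0.5 | 34/398 (9%) | 21/398 (5%) |
| rho 0.3, FWHM 3, effect 0.3 | 17/194 (9%) | 7/194 (4%) |
| rho 0.3, FWHM 3, effect 0.5 | 26/397 (7%) | 25/397 (6%) |
| FWHM 4, effect 0.32, rho 0.71 / 0.38 / 0.3 | 15% / 2% / 8% | not run |
| FWHM 4, effect 0.5, rho 0.3-0.71 | 2-8% | not run |
| FWHM 4, effect 0.96, rho 0.3-0.71 | 2-7% | not run |

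The Monte Carlo standard error is up to 3 points in the first row, up to 5 points at effect 0.32, and about 2 points in the last two rows. A further check with 60 replicates per setting gave about 5-29% at 0.3 SD and 2-7% at 0.5 and 0.96 SD. In the first-row settings, two-fold cross-fitting gave 0.065-0.071.

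**Size of the oscillatory effect read at the F-map peak.** In smooth images the ratio of observed to true effect was 1.31-1.48 at 0.28-0.35 SD, with a highest single value of 1.65 for a weak effect. In the FWHM 4 runs it was 1.06-1.11 at 0.5 SD and 1.02-1.06 at 0.96 SD.

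**The case against.** Several points on the other side have force.

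- **A different measure is tested.** Voxels are selected on response amplitude and the test is on baseline activity. At rho = 0 the error rate is 0.05. This stands, so excess error is a possibility and is not demonstrated. But both measures come from the same session, voxel and band, and a test should not depend for its validity on an unstated zero correlation.
- **The planned effect is large.** A between-subjects d of 0.96 becomes 0.96/sqrt(2(1 - r)) in SD of the paired difference, where r is the within-person correlation: 0.68 at r = 0 and 0.96 at r = 0.5. There the excess nearly vanishes. This also stands if the effect is localised. However, 0.96 is an average from a pilot, the documents do not say which measure it refers to, and they accept that the within-subject effect may not be larger.
- **The map is a gate.** If stimulation has no effect on oscillatory activity anywhere, a map controlled at 0.05 lets the second test run in at most about 5% of trials per band, which caps false spontaneous claims. This limits the large rates for false-positive clusters. It gives no cap when there is a true oscillatory effect.

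A reader might infer that the oscillatory findings are circular or overstated. The documents do not support that. Oscillatory inference rests on the corrected whole-brain map, the post-hoc tests are for direction, and no effect size at the peak is planned. Nor do they support saying that the spontaneous test is certainly too liberal.

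**Conclusion.** The concern holds in a conditional form. The plan selects the voxel by the condition contrast and tests the same contrast in the same sessions, so the spontaneous ANOVA can exceed 0.05 unless baseline and response contrast errors are uncorrelated. Under assumed correlations of 0.3 to 0.7, rejection among trials with a cluster is roughly 5-30% when the oscillatory effect is about 0.3 SD of the paired difference, and close to 5% for a localised effect of 0.5 SD or more (9% in the least favourable smooth-image run). Individual small runs scatter around these ranges. The figures rest on assumed correlation, smoothness and effect shape; smooth images have fewer effective voxels than the independent-voxel runs assume.

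The F-map inference is sound in this respect. An oscillatory effect size read at its peak would be biased upward, by about 1.5 times for weak effects and under 1.2 times in smooth images at 0.5 SD or more, but only if one were reported. This should be fixed because the outcome is central and the remedy is cheap; it does not invalidate the plan.

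**What to change.** Keep the F-map for whole-brain inference. For the spontaneous-activity ANOVAs, place the virtual sensors, per band, at the peak(s) of the response map averaged over anode, cathode and sham. With all three sessions per participant, that choice is essentially unrelated to the condition contrast. Place them whether or not an F-map cluster appears: restricting to trials with a cluster brings some selection back, which partly explains the 10% in one averaged-map run.

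If a sensor must lie in a stimulation-sensitive cluster, locate the peak in one random half of participants, take values from the other half, and swap. Leaving out one participant at a time is not a substitute, since dropping 1 of 124 hardly moves the peak: rejection was 0.17-0.30, against 0.20-0.30 without it, in 60-replicate runs with a standard error of about 5-6 points. Label any values taken at F-map peaks as descriptive. State whether amplitude is expressed relative to baseline.

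The cost is SAP wording and one averaged map per band, with no new data. The averaged-map peak may not be where stimulation altered the response most, so the question shifts slightly, and cross-fitting locates the peak less precisely.
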